3.7.2.2.1 Other significant AEs

The following categories for adverse events were selected based on effects that have been observed with olanzapine. The PTs to be included in each category were based on Standardized MedDRA queries (SMQs) or custom searches if the SMQs did not exist or were inadequate. These significant AEs will be summarized by the AE category, PT and treatment group.

- Extrapyramidal symptoms (list of PTs provided in Appendix)
- Nausea or vomiting (include these 2 PTs)
- Sedation (including sedation, somnolence, lethargy or hypersomnia)

3.7.3 Clinical Laboratory Parameters

Laboratory parameters will be presented in conventional units. Only laboratory results at the scheduled visits will be included in the summary tables. All lab data will be included in the listings.

Results will be summarized for hematology and chemistry by visit and the treatment group for Part A and Part B.

Additionally, for select parameters, number and percentage of subjects with values considered potentially clinically significant (PCS) occurring at any time post-baseline will be summarized

by treatment group. Criteria for PCS are presented in Table 1 and Table 2. Criteria for shift in lipids, glucose and HbA1c are presented in Table 3 and Table 4.

Table 1: Potentially Clinically Significant Results Criteria for Chemistry

Parameters	Criteria
Albumin	<2.5 g/dL
Alkaline phosphatase (U/L)	≥3 x ULN
Alanine Aminotransferase (U/L)	≥3 x ULN
Aspartate Aminotransferase (U/L)	≥3 x ULN
Alanine Aminotransferase (U/L)	≥3 x ULN
Bilirubin, Total	≥2.0 mg/dL
Blood Urea Nitrogen	>30 mg/dL
Cholesterol, Random	>300 mg/dL
Cholesterol, Fasting	≥240 mg/dL
Cholesterol, HDL fasting	≤30 mg/dL
Cholesterol, LDL fasting	≥160 mg/dL
Creatine Kinase (U/L)	≥3 x ULN
Creatinine	≥2.0 mg/dL
Glucose, Random	<50 mg/dL or ≥200 mg/dL
Potassium	<3 mmol/L or >5.5 mmol/L
Lactate Dehydrogenase (U/L)	>3 x ULN
Phosphate	<2 mg/dl or >5 mg/dl
Prolactin (Female)	>30 ng/mL
Prolactin (Male)	>20 ng/mL
Sodium	<130 mmol/L or >150 mmol/L
Triglycerides, fasting (Female)	≥120 mg/dL
Triglycerides, fasting (Male)	≥160 mg/dL

Table 2: Potentially Clinically Significant Results Criteria for Hematology

Parameters	Criteria
Eosinophils	$>1.0 \times 10^3/\text{uL}$
Hematocrit (Female)	$\leq 32\%$
Hematocrit (Male)	$\leq 37\%$
Neutrophils, Absolute	$<1.5 \times 10^3/\text{uL}$
Platelets	$<75.0 \times 10^3 \text{ cells/uL}$ or $\geq 700.0 \times 10^3 \text{ cells/uL}$
Leukocytes	$\leq 2.8 \times 10^3/\text{uL}$ or $\geq 16.0 \times 10^3/\text{uL}$

Table 3: Shifts Category in Lipid Parameters from Baseline to Any Post-Baseline.

Total cholesterol (fasting) mg/dL
Normal (<200) to High (≥ 240)
Borderline (≥ 200 and < 240) to High (≥ 240)
Normal/Borderline (<240) to High (≥ 240)
Normal (<200) to borderline/High (≥ 200)
Increase ≥ 40 mg/dL
LDL Cholesterol (fasting) mg/dL
Normal (<100) to high (≥ 160)
Borderline (≥ 100 and < 160) to high (≥ 160)
Normal/borderline (<160) to high (>160)
Normal (< 100) to borderline/high (≥ 100)
Increase ≥ 30 mg/dL
HDL Cholesterol (fasting) mg/dL
Normal (≥ 40) to low (<40)
Decrease ≥ 20 mg/dL
Triglycerides (fasting) mg/dL
Normal (<150) to high (≥ 200)

Normal (<150) to very high (≥ 500)
Borderline (≥ 150 and < 200) to high (≥ 200)
Borderline (≥ 150 and < 200) to very high (≥ 500)
Normal/borderline (< 200) to high (≥ 200)
Normal/borderline (< 200) to very high (≥ 500)
Normal (< 150) to borderline/high/very high (≥ 150)
Increase ≥ 50 mg/dL

Table 4: Shift Category in Glucose and HbA1c from baseline to any post-baseline

Serum glucose (fasting) mg/dL
Normal (< 100) to High (≥ 126)
Impaired (≥ 100 and < 126) to High (≥ 126)
Normal/Impaired (< 126) to High (≥ 126)
Increase ≥ 10 mg/dL
HbA1c (fasting) %
Shift from baseline ($< 6.1\%$) to: Post-baseline $\geq 6.1\%$
Post-baseline $\geq 8\%$
Post-baseline $\geq 10\%$
Post-baseline $\geq 12\%$

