5.3. Study Rationale

Schizophrenia is a lifelong illness and changes in medication are often made to better manage evolving symptoms and to control side effects and/or tolerability issues. Similar to what was done in the landmark CATIE study [Lieberman, 2005], this study is seeking to enroll patients that are psychiatrically stable, where stability is largely defined by the absence of significant fluctuations or an acute exacerbation of symptoms. In these patients, stability may still reflect a sub-optimal condition that could be improved by transitioning to a different medication. Other patients may be well-controlled on their current antipsychotic, but may be experiencing unpleasant or intolerable side effects such as hyperprolactinemia or extrapyramidal symptoms. These patients may also benefit from switching to a different medication.

In this Phase 2 study, such patients will be transitioned to olanzapine which is widely regarded as one of the most efficacious antipsychotics currently available. Patients with stable symptoms who are not currently taking an antipsychotic, but who may benefit from treatment with olanzapine, are also eligible to participate in this study. In addition to olanzapine, subjects will also receive samidorphan. Samidorphan may offer a range of potential benefits when administered with olanzapine for patients with schizophrenia including attenuated weight gain and a reduction in concomitant substance abuse. Both of these benefits have the potential to increase patient retention on therapy and improve long term outcomes.

One Phase 1 study, ALK33-301, has been conducted in healthy adults (N = 106) to determine the safety, tolerability, and efficacy of samidorphan taken with olanzapine to mitigate olanzapine-induced weight gain. The co-administration of samidorphan (5 mg) and olanzapine when administered once daily for 3 weeks to healthy volunteers was generally well tolerated and resulted in significantly less weight gain compared with subjects administered olanzapine alone. Aside from a positive effect on weight gain, samidorphan did not appear to impact the adverse event profile of olanzapine in this Phase 1 study. The co-administration of samidorphan and olanzapine did not impact the pharmacokinetics (PK) of either individual drug.

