- Personal or family history of neuroleptic malignant syndrome
 - Dyslipidemia, defined for this study as total cholesterol >280 mg/dL or triglycerides >500 mg/dL, at screening
 - Inflammatory bowel disease or any other gastrointestinal (GI) disorder associated with weight loss, anorexia nervosa, bulimia nervosa, or binge eating disorder
 - Neurologic conditions including the following:
 - History of seizure disorder or a condition associated with seizures
 - History of brain tumor, subdural hematoma or other clinically significant neurological condition within the 12 months prior to screening
 - Head trauma with loss of consciousness within the 12 months prior to screening
 - Active acute or chronic central nervous system (CNS) infection
 - Stroke within the 6 months prior to screening
8. Subject has a cardiac condition that might confound the results of the study or pose additional risk when administering the investigational agents to the subject or preclude successful completion of the study. Such conditions include the following:
- Clinically significant cardiac arrhythmia, cardiomyopathy, or cardiac conduction defect; a history of myocardial infarction or unstable angina; or clinically significant ECG abnormality at Visit 1 or Visit 2.
 - QT interval >450 msec for men and >470 msec for women, as corrected by the Fridericia formula (QTcF), observed at Visit 1 or Visit 2.
9. Subject has a laboratory abnormality that would compromise the well-being of the subject, or has any of the following specific laboratory results at Visit 1 or Visit 2:
- Aspartate aminotransferase (AST) or alanine aminotransferase (ALT) value ≥ 3 times the upper limit of the laboratory normal reference range
 - Absolute neutrophil count (ANC) $\leq 1.5 \times 10^3$ per μL at Visit 1 and $< 1.0 \times 10^3$ per μL at Visit 2
 - Platelet count $\leq 75 \times 10^3$ μL
 - Serum creatinine >2.5 mg/dL
 - Positive pregnancy test result
10. Subject is pregnant or breastfeeding or is planning to become pregnant within 60 days of the last study drug administration
11. Subject has had any GI surgical procedures within one year prior to screening
12. Subject has had a surgical procedure for weight loss or is planning to have liposuction during the study

13. Subject has had significant changes in diet or exercise regimen within the 6 weeks prior to screening or plans to join a weight management program during the study.

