3.1.1 Baseline Definition

Baseline for Part A is defined as the last non-missing observation on or before the first dose of study drug following randomization at Visit 3 (Day 8).

Baseline for Part B is defined as the last non-missing observation on or before the date of the first dose of study drug at Visit 13 (Day 92).

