3.11.3 Any Post-baseline Values

Any post-baseline values are defined as any valid values collected from scheduled or unscheduled visits, if applicable.

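### Laboratory PCS counts ignore baseline status, so for prolactin, creatinine, haematology, triglycerides and HDL they mix pre-existing abnormalities with new ones

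*SAP*

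**What the plan says.** SAP 3.7.3 provides that, for select parameters, the "number and percentage of subjects with values considered potentially clinically significant (PCS) occurring at any time post-baseline will be summarized" for each treatment group. Table 1 (chemistry) and Table 2 (haematology) give the limits, all as absolute values or multiples of the upper limit of normal. SAP 3.11.3 adds no baseline condition: "Any post-baseline values are defined as any valid values collected from scheduled or unscheduled visits, if applicable". The Part A baseline (SAP 3.1.1) is "the last non-missing observation on or before the first dose of study drug following randomization at Visit 3", so it follows one week of olanzapine.

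Two other parts of the SAP do look at baseline. Every vital-sign criterion in Table 5 (SAP 3.7.4) pairs a threshold with a minimum change. Tables 3 and 4 define shifts from baseline for fasting lipids, fasting glucose and HbA1c.

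Protocol 14.6 promises change-from-baseline summaries and shift tables for laboratory tests, with no restriction to particular analytes. The SAP writes shift criteria only for lipids, glucose and HbA1c, and SAP 3.10 declares no departure from the protocol's analyses.

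**The concern.** A PCS table is normally read as the incidence of new abnormalities on treatment. Under this rule a subject who was PCS at baseline and stays so counts exactly like one who became PCS after randomisation. That would matter little if the entry criteria kept such subjects out, but for several analytes they do not. The lipid exclusion reads "Dyslipidemia, defined for this study as total cholesterol >280 mg/dL or triglycerides >500 mg/dL, at screening", well above the fasting PCS limits. Protocol 5.3 names patients with "hyperprolactinemia or extrapyramidal symptoms" on their current drug as candidates to switch, so raised prolactin at entry is foreseen.

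At stake is how readable the safety incidence tables are. Background cases enter all arms alike and make any difference between arms look smaller than it is among subjects who could newly develop the abnormality.

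**Working it through.** **Step 1. Entry limits (Protocol 7.2) against PCS limits (SAP Tables 1 and 2).**

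| Analyte | Excluded at entry | PCS limit | PCS at baseline possible? |
|---|---|---|---|
| Creatinine, mg/dL | >2.5 | ≥2.0 | Yes, 2.0-2.5 |
| Neutrophils, ×10³/µL | ≤1.5 at Visit 1, <1.0 at Visit 2 | <1.5 | Yes, 1.0 to <1.5 at Visit 2 |
| Triglycerides, mg/dL | >500 at screening (non-fasting) | fasting ≥120 (F), ≥160 (M) | Yes, up to 500 |
| Total cholesterol, mg/dL | >280 at screening (non-fasting) | fasting ≥240; random >300 | Fasting yes; random not at screening |
| Prolactin, ng/mL | none | >30 (F), >20 (M) | Yes |
| LDL; HDL, mg/dL | none | fasting ≥160; ≤30 | Yes |
| Hematocrit, eosinophils, leukocytes | none | Table 2 | Yes |
| AST, ALT | ≥3 × ULN | ≥3 × ULN | Not at entry visits |
| Platelets, low, ×10³/µL | ≤75 | <75 | Not at entry visits |
| Random glucose, high, mg/dL | ≥200 at Visit 1 | ≥200 | Not at Visit 1 |

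Because baseline is Visit 3, a value that becomes abnormal during the olanzapine lead-in is also abnormal at baseline, even for the last three rows.

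**Step 2. What the shift tables already cover.**

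- Fasting cholesterol: the shift from <240 to ≥240 is a new-case count at exactly the PCS limit.
- LDL: there is a shift category at 160, in effect the PCS limit.
- Glucose and HbA1c: covered by Table 4.
- Triglycerides: shift limits are 150, 200 and 500; PCS limits are 120 (women) and 160 (men). No match.
- HDL: the shift limit is <40; the PCS limit is ≤30. No match.
- Prolactin, creatinine, haematology: no shift criteria in the SAP.

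Also, a woman with fasting triglycerides of 120-149 mg/dL is PCS in Table 1 and normal in Table 3.

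**Step 3. Direction and possible size.** The plan gives no figure to reproduce. Let b be the share PCS at baseline, s the share of those still PCS afterwards, and p the onset risk in the remainder. Then

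observed risk = b·s + (1 − b)·p.

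If b and s are the same in two arms, the b·s term cancels:

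observed difference = (1 − b) × (p₁ − p₂).

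The documents give none of b, s or p. As an illustration, assume onset risks of 10% and 20% (difference 10 points, ratio 2.00) and s = 1:

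| b | Observed risks | Difference, points | Ratio |
|---|---|---|---|
| 5% | 14.5% vs 24.0% | 9.5 | 1.66 |
| 10% | 19.0% vs 28.0% | 9.0 | 1.47 |
| 20% | 28.0% vs 36.0% | 8.0 | 1.29 |
| 40% | 46.0% vs 52.0% | 6.0 | 1.13 |

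For b = 20%: 0.20 + 0.80 × 0.10 = 0.28 and 0.20 + 0.80 × 0.20 = 0.36. With s = 0.8 at the same b: 0.16 + 0.08 = 0.24 against 0.16 + 0.16 = 0.32, ratio 1.33. Restricting to subjects not PCS at baseline recovers 10% vs 20% in every row.

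**The case against.** The strongest reply is that the metabolic objective does not rest on PCS counts. The protocol's metabolic endpoints are changes in lipids and glucose measures, and Tables 3 and 4 condition on baseline for exactly those. Their fixed-change categories, such as a triglyceride rise of at least 50 mg/dL, also capture worsening in subjects already abnormal, whom a restricted denominator would drop. This stands. A reader might infer from the PCS rule that the plan has no treatment-emergent view of metabolic effects; the documents do not support that.

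A reader might also infer bias between arms or a loss of power. Neither follows. Part A is randomised and baseline precedes randomised treatment, so the background share is the same across arms in expectation. The SAP plans no test of PCS counts, so there is no power to lose.

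Nor are all analytes affected: matching entry limits protect AST, ALT, low platelets and high random glucose at the entry visits. Out-of-range values judged clinically significant are also recorded as adverse events (Protocol 13.2), and all laboratory data are listed. Those routes help, but one depends on investigator judgement and the other is not a summary.

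The general promise of shift tables in Protocol 14.6 narrows the gap only if it is carried out. The SAP specifies nothing for prolactin, creatinine or haematology.

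**Conclusion.** The point holds in a limited form. The laboratory PCS counts take no account of baseline, and the entry criteria admit subjects already past several limits. No matching baseline-conditioned count is specified for prolactin, creatinine or haematology, nor for triglycerides and HDL at their PCS limits.

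The effect is attenuation of a descriptive contrast by the factor (1 − b). This rests on equal persistence across arms. If treatment changed how often baseline abnormalities resolve, the difference would gain a further term of b times the difference in persistence, and the net direction could change. The actual size cannot be computed because baseline prevalence is not given; the ratios above illustrate assumed values only. For rarely abnormal analytes the loss is small, and for common ones it could be marked. Efficacy conclusions are untouched. This is a worthwhile, inexpensive improvement to the safety tables, not a flaw in the trial.

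**What to change.** In SAP 3.7.3, report post-baseline PCS values among subjects who were not PCS at baseline for that parameter and have one or more post-baseline values, and state that number as the denominator. List subjects who were PCS at baseline separately by arm, so that persistence or worsening among them is not lost. If the count is also produced for Part B, state which baseline applies.

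Add the shift tables promised in Protocol 14.6 for prolactin, creatinine and haematology. Reconcile the Table 1 triglyceride limit for women with the normal range in Table 3.

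No new data are needed. The cost is smaller denominators, reduced by the baseline PCS share. At an assumed 20%, 70 per arm becomes 70 × 0.80 = 56; at 40% it becomes 70 × 0.60 = 42. The reduction may be substantial for triglycerides or prolactin.

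### The SAP's limit for potentially clinically significant fasting triglycerides in women (≥120 mg/dL) lies inside the range that the same section calls normal (<150 mg/dL)

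*SAP*

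**What the plan says.** SAP 3.7.3 (Clinical Laboratory Parameters) reports triglycerides against two sets of cut-offs.

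- **Table 1 (PCS criteria, chemistry).** The row that begins "Triglycerides, fasting (Female" has a limit of ≥120 mg/dL. The row that begins "Triglycerides, fasting (Male" has ≥160 mg/dL.
- **Table 3 (lipid shifts).** The categories have no split by sex. The row "Normal (<150) to high (≥ 200" fixes normal as below 150 and high as 200 or above. The row "Borderline (≥ 150 and < 200) to high (≥ 200" fixes the band between them as borderline. Very high starts at 500.

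For selected parameters the section summarises, by treatment group, the "number and percentage of subjects with values considered potentially clinically significant (PCS) occurring at any time post-baseline". Table 1 sets no condition on the baseline value or on the change from it.

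Entry does not remove raised triglycerides below an extreme level. Protocol 7.2 excludes "Dyslipidemia, defined for this study as total cholesterol >280 mg/dL or triglycerides >500 mg/dL, at screening".

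**The concern.** One section of one plan gives two incompatible labels to the same laboratory value. A woman whose fasting triglyceride is 130 mg/dL throughout would appear in the PCS table, while the shift table would treat her as normal at every visit. The SAP gives no reason for the lower female limit and does not say how the two tables relate.

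Metabolic effect is the third study objective, and change in triglycerides is listed in Protocol 13.1. A reader of the PCS table will want to know what a flagged subject represents. As written, a flag in a woman can mean anything from a normal, unchanged value to a very high one. A flag in a man means at least borderline. The PCS table is by treatment group, and Protocol 9.3 stratifies randomisation by lead-in weight change, not by sex. The reported percentage therefore also reflects how many women each arm happens to contain.

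**Working it through.** There is no stated figure to reproduce, because the point concerns two sets of cut-offs. The check has three steps.

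**1. Classify values under both tables.**

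| Fasting triglyceride (mg/dL) | Table 3 class | PCS, woman (≥120) | PCS, man (≥160) |
|---|---|---|---|
| 119 | normal | no | no |
| 120 | normal | **yes** | no |
| 149 | normal | **yes** | no |
| 150 | borderline | yes | no |
| 159 | borderline | yes | no |
| 160 | borderline | yes | yes |
| 199 | borderline | yes | yes |
| 200 | high | yes | yes |

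The overlap of normal and PCS is 120 to <150 mg/dL, in women only. No male value is both.

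**2. Compare with the other fasting lipids.**

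| Lipid | Table 1 PCS limit | Table 3 categories | PCS limit inside normal? |
|---|---|---|---|
| Total cholesterol | ≥240 | "Normal (<200) to High (≥ 240" | no; equals high |
| LDL | ≥160 | "Normal (<100) to high (≥ 160" | no; equals high |
| HDL | ≤30 | normal ≥40, low <40 | no; stricter than low |
| Triglycerides, men | ≥160 | borderline 150 to <200 | no; in borderline |
| Triglycerides, women | ≥120 | normal <150 | **yes** |

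**3. Gauge the size.** The documents give no triglyceride distribution, so this step rests on an assumption: log-normal values in women, median *m* of 90 to 130 mg/dL, geometric SD *g* of 1.5 or 1.7, one sample per woman.

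P(TG ≥ x) = 1 − Φ(ln(x/m) / ln g)

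Share of flagged women who are normal by Table 3 = (P(≥120) − P(≥150)) / P(≥120)

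| m | g | P(≥120) | P(≥150) | P(≥200) | Share normal among flagged |
|---|---|---|---|---|---|
| 90 | 1.5 | 0.239 | 0.104 | 0.025 | 0.57 |
| 110 | 1.5 | 0.415 | 0.222 | 0.070 | 0.46 |
| 130 | 1.5 | 0.578 | 0.362 | 0.144 | 0.37 |
| 90 | 1.7 | 0.294 | 0.168 | 0.066 | 0.43 |
| 110 | 1.7 | 0.435 | 0.279 | 0.130 | 0.36 |
| 130 | 1.7 | 0.560 | 0.394 | 0.208 | 0.30 |

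First row worked: ln(120/90)/ln 1.5 = 0.710, which gives 0.239. ln(150/90)/ln 1.5 = 1.260, which gives 0.104. The share is (0.239 − 0.104)/0.239 = 0.57.

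Across this range 24–58% of women would be flagged, and 30–57% of those flagged would be normal by Table 3. A second assumed grid (median 80–120, log-SD 0.4–0.6) gives a share of 29–63%.

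Dependence on sex mix follows from the definition. If *f* is the fraction of women in an arm, its PCS proportion is f × P(woman ≥120) + (1 − f) × P(man ≥160). It shifts with *f* whenever those two probabilities differ.

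**The case against.** The best defence is that the two tables do different jobs. Table 1 flags single values, with sex-specific limits for some analytes; Table 3 counts movements from baseline. The SAP never says they share limits, and HDL shows that a PCS limit need not coincide with a Table 3 category. Triglycerides are also reported by visit and arm, in seven shift categories and in a category for a rise of at least 50 mg/dL, so metabolic interpretation does not rest on this row. All of this stands, and it keeps the point small. It does not explain why a value the section calls normal should be flagged as potentially clinically significant.

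A reader might also infer three stronger things that the documents do not support.

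- **That the low limit hides a treatment difference.** The SAP reports numbers and percentages by arm. Under the same log-normal, suppose one arm's median is 15% or 25% higher (medians 90, 110, 130; geometric SD 1.5, 1.7; 12 scenarios). The between-arm difference in percentage flagged among women is larger at ≥120 than at ≥200 in all 12. With median 90, geometric SD 1.5 and +15%, it is 11.9 against 2.8 points. With median 110, geometric SD 1.7 and +25%, it is 16.6 against 11.0 points. Only the ratio of percentages is smaller at the lower limit, and the SAP does not plan a ratio.
- **That it overstates metabolic harm from treatment.** The limit is the same in every arm, so it raises the count under olanzapine alone as well.
- **That both triglyceride rows should move to Table 3's high limit.** The male limit falls in the borderline band, and borderline does not contradict PCS.

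**Conclusion.** The inconsistency is certain, because it can be read directly from the two tables. It covers women at 120 to <150 mg/dL and nothing else among the fasting lipids. Its consequence is a PCS percentage for triglycerides that mixes values of different meaning and varies with an arm's sex mix.

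The size is uncertain. The 30–57% of flagged women who would be normal by Table 3 comes wholly from the assumed distribution, and the documents also give no expected sex mix.

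The table is descriptive. No primary or secondary efficacy analysis, error rate or power figure depends on it, and there is no between-arm bias. Severity: minor.

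**What to change.** Before unblinding, reconcile the female triglyceride row of SAP Table 1 with Table 3 so that no value is both normal and PCS. That means the PCS limit must not fall below Table 3's upper limit of normal; the sponsor should choose the limit. If the sex-specific limit is kept, state the reason for it and report triglyceride PCS separately for women and men. The male row need not change.

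The cost is an edit to one table cell, or a sentence of justification and a split by sex. No new data are needed. If the limit is raised, fewer women are flagged: at 150 mg/dL, the lowest limit that removes the overlap, 10–39% under the assumed distribution instead of 24–58%. Smaller rises remain visible in the by-visit summaries and, from 50 mg/dL upward, in Table 3's increase category.
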